10.1.1.2 Analysis of Covariance (ANCOVA)

The continuous efficacy variable (such as brain volume percent change from baseline) will be analyzed using an ANCOVA model adjusted for treatment, region, pubertal status (the stratification factor in IVRS), and baseline disease characters as appropriate.

Below is an example of the SAS codes to perform the ANCOVA model.

```
*****  
* SAS Codes: ANCOVA model  
* Variables in the model:  
* PBVC = percent brain volume change from baseline  
* trt = treatment group code  
* reg1a = region code  
* Pbt = puberty status  
* bl = baseline character  
* NBV = baseline Normalized brain volume at baseline  
*****;  
proc mixed data=data1;  
  class trt reg1a pbt;  
  model PBVC = trt reg1a pbt NBV;  
  lsmeans trt /pdiff cl om;  
  ods output lsmeans=lst;  
run;
```

10.1.1.3 Rank Analysis of Covariance (ANCOVA) and Rank Analysis of Variance (ANOVA)

Rank Analysis of Covariance (ANCOVA)

The rank ANCOVA is a non-parametric statistical method described in (Stokes, Davis, and Koch 2000). It can be considered as an extension to the Wilcoxon rank-sum test with the ability to adjust for covariates in the model.

The analysis can be easily implemented using SAS by the following three steps: 1) to compute the ranks of the response variable and covariate in the combined group of treatment using PROC RANK; 2) to calculate the residuals from the linear regression of the response variable ranks vs. ranks of the covariates (without treatment) using PROC REG; 3) the CMH mean score statistics is used to compare the mean values of the residuals in treatment using TABLE scores (default scores) in PROC FREQ. Below is an example of the SAS codes used to perform this rank ANCOVA.

```
*****  
* SAS Codes: Rank ANCOVA model  
* Variables in the model:  
* VolGd =volume of Gd-enhancing lesions  
* trt = treatment group code
```

```

* reg1a = region code
* Pbt = puberty status
* blvGd = baseline volume of Gd-enhancing lesions
* sid1a = subject ID
*****;
Data eff;
  Set eff;
  If reg1a = ' ' or blvGd = . or Pbt = . or VolGd = . then delete;
run;
proc rank data=eff nplus1 ties=mean out=ranks;
  by reg1a pbt;
  var blvGd VolGd;
run;
proc reg data=ranks noprint;
  by reg1a Pbt;
  model VolGd=blvGd;
  output out=residual r=resid;
run;
proc freq data=residual;
  tables reg1a*pbt*trt*resid / noprint cmh2;
  where trt in ('A', 'B');
  output out=rancova cmh2;
  *** SELECT P_CMHRMS;
run;

```

10.1.1.4 Logistic regression for proportion variables

The other secondary/other efficacy variables (proportion of patients free of relapses, proportion of patients free of new or newly enlarging T2 lesions, proportion of patients free of Gd-enhanced T1 lesions, proportion of patients free of new MRI activity) will be analyzed using the logistic regression model adjusted for treatment, region, and other corresponding covariates, on the full analysis set.

Logistic regression is a model for prediction of the probability of occurrence of an event. It can be used to analyze the dichotomous response data while adjusting for one or more covariates. Usually, Logistic regression analyzes binomially distributed data of form

$$Y_i \sim B(n_i, p_i), \text{ for } i=1, \dots, n.$$

The logits of the unknown binomial probabilities (i.e., the logarithms of the odds) are modeled as a linear function of the X_i . $\log\left(\frac{p_i}{1-p_i}\right) = \beta_0 + \beta_1 x_{1,i} + \dots + \beta_k x_{k,i}$

Below is an example of the SAS codes to perform the analysis of the LOGISTIC regression.

```

*****
* SAS Codes: LOGISTIC model
* Variables in the model:
* mrfree = proportion of patients free of Gd-enhanced T1 lesions
* reg1a = region code

```

```
* pbs=pubertal status at baseline
* blmri = baseline number of Gd-enhanced T1 lesions
*****.
proc logistic data=eff descending;
  class reg1a pbs trt /param=ref;
  model mrifree = reg1a pbs trt blmri;
  contrast 'A - B' trt 1 /estimate=exp;

  ods output Contrastestimate=est;
run;
```

10.1.1.5 Survival analysis for time to event variables

Log-rank test will be used to compare the survival distributions of two treatment groups for secondary efficacy time to event variables, for example time to first confirmed relapse. The analyses were performed on the full analysis set.

The log-rank test statistic compares estimates of the hazard functions of the two groups at each observed event time. It is constructed by computing the observed and expected number of events in one of the groups at each observed event time and then adding these to obtain an overall summary across all time points where there is an event.

Cox proportional hazards model is to estimate the effect parameter(s) without any consideration of the hazard function assuming the proportional hazards assumption holds. The proportional hazards assumption is the assumption that effect parameters multiply hazard: for example, if taking drug X halves your hazard at time 0, it also halves your hazard at time 1, or time 0.5, or time t for any value of t. The effect parameter(s) estimated by any proportional hazards model can be reported as hazard ratios. Below is an example of the SAS codes to perform the Log-rank test with Kaplan-Meier Method and the Cox proportional hazards model.

```
*****
* SAS Codes: LOG-RANK test with Kaplan-Meier Method
* Variables in the model:
* reltm = time to first confirmed relapse
* trt = treatment group code
* relcens = censor flag (1=censored, 0=not censored)
*****.
proc lifetest data=eff method=km;
  where trt in ('A', 'B');
  time reltm*relcens(1);
  strata trt;
run;
*****
* SAS Codes: Cox's regression model
* Variables in the model:
* reltm = time to first confirmed relapse
* trt = treatment group code
```

```

* reg1a = region code
* n2 = number of relapses within the previous 2 years before randomization
* bledss = baseline EDSS
* relcens = censor flag (1=censored, 0=not censored)
*****;
proc phreg data=datain nosummary;
  class trt reg1a/ order=internal parm=GLM;
  model reltm*relcens(1)=trt n2 bledss reg1a/rl ties=exact;
  contrast "A vs B" trt 1 -1/estimate=exp;

ods output parameterestimates=pest;
ods output contrastestimate=est;
run;

```

**Note that data set pest contains Hazard ratio estimates from model statement. If parameter='trt', then SELECT probchisq hazardratio hrlowercl hruppercl for results;

**However, data set est contains Hazard ratio estimates from contrast statement (result variable names: estimate lowerlimit upperlimit probchisq);

Estimation of 95% confidence intervals

Approximate 95% confidence intervals will be generated for several estimates: (1) at selected time-points, the (Kaplan and Meier 1958) estimates of the proportion of patients experiencing a specific event, (2) at selected time-points, the between-treatment group difference in Kaplan-Meier estimates of the proportion of patients experiencing a specific event. Details of such confidence intervals are displayed in Table 2-1.

Table 2-1 Confidence Interval calculations

	Approximate Confidence Interval (CI)	Lower Limit	Upper Limit
1	x% CI for the Kaplan-Meier estimate KM Notation: SE = estimated standard error of KM ; estimation of standard error uses Greenwood's formula, $c_x = \Phi^{-1}(\frac{1}{2} + x/200)$, where Φ is the normal distribution function.	$KM - c_x * SE$	$KM + c_x * SE$
2	x% CI for the difference in Kaplan-Meier estimates $KM_2 - KM_1$ Notation: KM_i = Kaplan-Meier estimate for group $i = 1, 2$, $SE_d = \sqrt{SE_1^2 + SE_2^2}$, where SE_i^2 = estimated standard error of KM_i , $i = 1, 2$; estimation of standard error uses Greenwood's formula, $c_x = \Phi^{-1}(\frac{1}{2} + x/200)$, where Φ is the normal distribution function.	$KM_2 - KM_1 - c_x * SE_d$	$KM_2 - KM_1 + c_x * SE_d$
Examples: for $x = 95$, $c_x = \Phi^{-1}(0.975) = 1.95996$; for $x = 97.5$, $c_x = \Phi^{-1}(0.9875) = 2.24140$			

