4.2.2.3.1 Time to first relapse and proportion of relapse-free subjects

Time to first relapse and proportion of relapse-free subjects are considered as other secondary endpoints related to relapses.

For subjects with at least one event (i.e., relapse), time to event is calculated as (event start date – 1st core dose date + 1). For subjects without event, time to event will be calculated the same as the time in study for ARR in [Section 4.1.2](#).

The log-rank test of the treatment difference in the Kaplan–Meier estimates of the survival function of the time to first relapse will be performed.

Kaplan-Meier (KM) estimates of the survival functions will be constructed by treatment group. KM estimates of the relapse free patients at 12 and 24 months, together with 95% confidence intervals will be presented. Two-sided 95% confidence intervals of the difference in KM estimates will also be presented. The corresponding KM plot will be provided.

Cox’s proportional hazards model adjusted for treatment, region, pubertal status (the stratification factor in IVRS), and number of relapse within the previous two year before randomization will be performed as a supportive analysis. Estimates of the hazard ratio and its 95% confidence intervals, and the p-value for treatment comparison from the Cox model will be provided.

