9.1 Sample size calculations

The sample size calculations are based on the primary efficacy variable, the annualized relapse rate (ARR). The sample size calculations and power considerations follow the method outlined in Keene et al, 2007 with a constant dispersion parameter k and were programmed manually using the SAS software.

Different scenarios of the anticipated treatment effect between fingolimod versus IFN β -1a, have been evaluated based on the available data on fingolimod and on IFN β -1a in the Phase III program in adults. In the TRANSFORMS study (FTY720D2302), a double-blind, one-year study, fingolimod 0.5 mg was directly compared to interferon beta-1a i.m. The ARR (0.21) in patients treated with fingolimod 0.5 mg was reduced by 52% compared to the ARR (0.43) in patient treated with INF beta-1a.

The initial assumptions for this study (based on adult patient data) was as follows: assuming a 50% relative reduction (from 0.72 to 0.36) in the relapse rate over 24 months (ARR: $\lambda_1=0.18$ for fingolimod, $\lambda_2=0.36$ for interferon beta-1a), a sample size of 95 patients per treatment group (or 190 total) would be needed for a study with a fixed follow-up of 24 months in order to provide 80% statistical power at a two-sided alpha level of 0.05 (with dispersion parameter of $k=0.82$). This corresponds to a statistical information $I=16.36$.

The core phase of the study was amended so that when the information for the blinded data review exceeds the required value of 16.36 (i.e. $I>16.36$) which corresponds to the targeted power for the primary statistical test, all subjects who are ongoing in the core phase will be scheduled for the end of treatment/study visit. Any data collected during follow up but after the core phase data base lock will be reported in the extension phase CSR.

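### Per-arm Kaplan-Meier relapse-free limits use an untransformed Greenwood interval, which can under-cover slightly at Month 24 if the core phase ends early; log-log limits on S(t) do better at the same width

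*SAP*

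**What the plan says.** SAP Section 4.2.2.3.1 plans that "KM estimates of the relapse free patients at 12 and 24 months, together with 95% confidence intervals will be presented". It adds: "Two-sided 95% confidence intervals of the difference in KM estimates will also be presented". Section 10.1.1.5 gives the method. It describes the limits as approximate ("Approximate 95% confidence intervals will be generated for several estimates"), and its Table 2-1 has two rows:

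- Row 1, single arm: KM ± c × SE, where "estimation of standard error uses Greenwood's formula" and c = 1.95996 for 95%.
- Row 2, difference: KM₂ − KM₁ ± c × SE_d, with SE_d the root of the summed squared standard errors.

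Neither row has a transformation or bounds the limits to 0–1. The example PROC LIFETEST code in the same section sets no interval type. Section 4.2.2.3.1 works with the relapse-free proportion, whereas Section 10.1.1.5 speaks of the proportion with the event.

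Protocol Section 4 sets a core-phase maximum of about two years and no minimum. Under SAP Section 9.1, once the blinded information exceeds 16.36 all ongoing patients are called for their final visit.

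**The concern.** The untransformed interval is symmetric, but the sampling distribution of a Kaplan-Meier estimate is skewed when the risk set is small. Month 24 is the end of follow-up, so its risk set is the smallest of the curve. A core phase that stops on information rather than on time can make it smaller still. The interval method does not allow for this, although the SAP postdates the change in design.

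The proportion relapse-free is a named secondary objective. What is at stake is the accuracy of its reported per-arm intervals, and in particular a lower limit that overstates how many patients stay free of relapse. No hypothesis test is at stake.

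**Working it through.** **1. The plan's own figures.** Inputs from SAP Section 9.1: 95 per arm, annualized relapse rates 0.18 and 0.36, dispersion κ = 0.82, T = 2 years, and "80% statistical power at a two-sided alpha level of 0.05". With equation 2 of protocol Appendix 5:

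I = 95 / [1/(0.18×2) + 1/(0.36×2) + 2×0.82] = 95 / (2.778 + 1.389 + 1.640) = 16.36, as stated.

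Power = Φ(0.6931 × √16.36 − 1.960) = Φ(0.844) = 80.1% (stated: 80%).

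The documents give no coverage figure for the Kaplan-Meier intervals.

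**2. True relapse-free proportions.** The gamma-frailty form of the negative binomial gives S(t) = (1 + κλt)^(−1/κ). At t = 2:

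- Fingolimod: (1 + 0.82×0.18×2)^(−1/0.82) = 1.2952^(−1.2195) = 0.729.
- Interferon: 1.5904^(−1.2195) = 0.568.

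**3. One interval by hand.** Take S = 0.7295, n = 95 and no censoring. SE = √(0.7295×0.2705/95) = 0.0456.

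- Plain: 0.7295 ± 1.96×0.0456 = 0.640 to 0.819.
- Log-log: S^exp(±1.96×SE/|S ln S|), with 1.96×0.0456/0.2301 = 0.388, gives 0.7295^1.474 to 0.7295^0.678 = 0.628 to 0.807.

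The width is 0.179 either way. The log-log interval is moved down.

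**4. Coverage at Month 24.** Simulation with 95 per arm and first-relapse times from step 2. An assumed share can reach Month 24 and the rest are censored uniformly over Months 3–24. Monte Carlo error is about 0.3–0.5 points. Expected number at risk = 95 × share × S(24). Coverage ranges run across the two arms.

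| Share able to reach Month 24 (assumed) | At risk, fingolimod / interferon | Coverage, plain limits | Shortfall from 95% (points) |
|---|---|---|---|
| one half | 34.6 / 27.0 | 93.7–94.4% | 0.6–1.3 |
| one quarter | 17.3 / 13.5 | 93.2–93.7% | 1.3–1.8 |
| one tenth | 6.9 / 5.4 | 90.9–92.1% | 2.9–4.1 |

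Log-log limits cover 94.0–95.4% over the same settings.

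The censoring pattern matters somewhat. If the rest are censored earlier (uniformly over 0.2–1.75 years), the results are:

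| Arm | Plain, half / quarter | Log-log, half / quarter |
|---|---|---|
| Fingolimod | 93.9% / 92.7% | 95.0% / 94.3% |
| Interferon | 94.3% / 93.5% | 95.1% / 94.8% |

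**5. Direction.** Nominal misses are 2.5% on each side. At the fingolimod rate with a quarter reaching Month 24, the true value lies below the plain lower limit in 6.2% of runs and above the upper limit in 1.2%. With a tenth, it is 7.4% and 0.9%.

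**6. Month 12 and the difference.** At Month 12, plain limits cover 93.2–95.0% and log-log limits 94.5–95.4%. The row 2 difference interval covers 94.0–94.8% when 20–50% reach Month 24, and a variance-recovery interval built from log-log limits covers 94.3–95.4%. With 5–10% reaching Month 24 the figures are 92.0–93.9% and 92.8–93.5%.

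**7. How many reach Month 24?** Not stated. The Amendment 7 rationale reports more than 100 randomized by 28 September 2015 and a possible stop by June 2017. Enrollment was expected to start around Amendment 2 (July 2013). If accrual was linear (an assumption), about 100 × 23.6/26.6 ≈ 89 patients had entered by the end of June 2015. That is 89/190 = 47% with 24 months of potential follow-up, before dropout.

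**The case against.** Plain Greenwood limits are a recognised, fully prespecified method, and the SAP itself calls the intervals approximate. The endpoint is an other secondary one, outside the two-step hierarchy of SAP Section 4.2.2.1. The treatment comparison uses the log-rank test and the Cox model, and neither uses these limits. All of that stands, and it is why the point is minor.

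The objection also answers four stronger readings that a reader might infer:

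- **That few patients will reach Month 24.** The documents do not establish this. Early completion depends on the blinded information. If the target is missed, the Amendment 7 summary has the study run the full two years. The accrual dates are compatible with nearly half reaching Month 24.
- **That limits will exceed 100%.** At the planning rates, with a quarter or a half reaching Month 24, this happened in 0 of 4,000 runs in either arm. It needs a relapse-free proportion well above the planned 73%, whereas Amendment 7 reports relapse rates higher than assumed.
- **That the difference interval is also too narrow.** Its coverage is close to nominal when 20–50% reach Month 24 (step 6), and variance recovery adds little.
- **That log-log limits restore 95% in every case.** They do not. Under staggered entry with 0–5% reaching Month 24 (0–3 at risk), log-log limits cover 89.9–93.3% against 88.4–91.1% for plain limits. They are undefined at KM = 0 or 1, and could not be computed in up to 2.3% of those runs.

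The per-arm result remains. In every setting with partial follow-up the plain interval covers less than the log-log interval, with its misses mainly at the lower limit when the risk set is small.

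**Conclusion.** The point holds for row 1 of Table 2-1 only. The untransformed per-arm limits can under-cover at Month 24 if the core phase ends early. At the planning rates the shortfall is about 1–2 points when a quarter to a half of patients can reach Month 24, and about 3–4 points when about a tenth can. Most of the error is an optimistic lower limit.

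These sizes rest on the planning rates, dispersion 0.82, 95 per arm and an assumed share and pattern of censoring. If everyone is followed to Month 24, little is left to correct. The conclusion concerns the description of one secondary endpoint. It does not touch the sample size or any planned test.

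**What to change.** 1. In Table 2-1 row 1, specify log(-log) limits computed on the relapse-free probability S(t). State the scale, because the transformation gives different limits on the event proportion and the SAP uses both descriptions.
2. Set that interval type explicitly in the PROC LIFETEST example, so that the output follows the table and not a default.
3. Report the numbers at risk at Months 12 and 24 beside the estimates.
4. Say what is shown when KM is 0 or 1, where log-log limits do not exist.
5. Leave row 2 as planned.

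The cost is a few words of SAP text and one procedure option. Mean width is essentially unchanged (for example 0.241 plain against 0.243 log-log). When almost nobody is at risk neither interval is reliable, and the numbers at risk will let the reader see that.

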10.1.1.6 Between-treatment group comparisons on baseline variables

For baseline comparability analysis, categorical variables will be analyzed by Cochran-Mantel-Haenszel (CMH) test stratified by region and pubertal status; continuous variables will be analyzed using ANOVA with covariates of treatment, region, and pubertal status.

* SAS Codes: CMH

```
* Variables in the model:
* trt = treatment group code
* reg1a = region code
* Pst =Pubertal status
*****;
proc freq data=temp;
  tables reg1c*trt*(list of baseline categorical variables)/cmh;
run;

*****
* SAS Codes: ANOVA
* Variables in the model:
* trt = treatment group code
* reg1a = region code
* Pst =Pubertal status
*****;
proc glm data=temp;
  class tgpla reg1c pst;
  model list of baseline continuous variables =trt reg1c Pst;
run;
```
